5 QUALITY ASSURANCE

5.1. Procedures in Place to Ensure the Validity and Integrity of the Data

Quality Assurance of data entry and data management consists of a set of proactive tools that are implemented to increase the quality of the data processing components including: (1) Form design to avoid structural missingness, orphan questions, and as many "write-in" responses as possible; (2) Training of the data entry operators on the study forms so that they are familiar with the required responses; (3) Design of the data entry screens to look as much like the paper forms as possible; (4) Specifications of the data fields to reflect the nature of the data to be entered; (5) Specification of the edit parameters and checking algorithms so that every field is verified as completely as possible; and (6) Validation of the database system to certify that data entered into the data entry screens are accurately recorded in the databases.

In other areas, quality assurance will be implemented in a variety of ways: (1) Training of the research staff on data collection techniques with periodic retraining; and (2) Immediate review of data collection to be sure that data collection forms are fully complete. All staff will be trained on the protocol and issued certification numbers for the study. Staff will have to be certified in an area (such as data entry and patient

randomization) before the study systems will allow them to perform those tasks. All study systems will require a dual level login procedure for each task.

5.2. Procedures to Guarantee the Accuracy and Completeness of the Data, During Data Collection, Entry, Transmission, and Analysis

For quality control measures, regular analyses will report on: (1) Number of missing data items; (2) Number and type of forms that are failing edit; and (3) Distribution of data to look for outliers. A Quality Control report will be generated at the same time as the DSMB report for review by study leadership and by the DSMB. In addition to the quality assurance/quality control plans for data entry described above, we will select a 10% sample of patients each quarter to review select (high-risk) data for verification against source documents, including patient characteristics and laboratory assay results. Any item discrepancies of greater than 2% will be discussed with the site data coordinator and retraining/additional observation instituted if required.

Only research team members will have access to subject identifying information, which will be stored electronically only in the participant tracking database in the U Mass Medical School regulated environment. Each patient will be identified with a study ID number which will be used on all data collection forms. Only the participant tracking database will have the link between the study ID number and the PII of the patient.

5.3 Monitoring Missing Data

Reports on missing data will be reviewed by the DSMB, including missing forms and missing data items. In addition, for data that are missing, we will consider appropriate imputation procedures, such as model-based multiple imputation, for study analyses. To identify spurious data, we will implement edit checks at data entry for values that are out of normal range, inconsistent values, and improper data entry so that most problems will be detected during data entry. Additional edit checks will be implemented to run when the data are submitted to the main study database. These will include edits across visits and across forms, so that large changes between visits and inconsistent responses between case report forms will generate an edit query. Edit queries will be forwarded to the appropriate clinical site coordinator for resolution through changes done through REDCap. The implementation of REDCap at University of Massachusetts Medical School has the audit trail fully implemented so that any changes to the original submitted data are recorded and documented.

6 **REGULATORY ISSUES**

6.1. Reporting of Serious Adverse Events (SAE) and Suspected Adverse Reactions (SAR)

With regard to serious adverse events and suspected adverse reactions, both expected and unexpected and regardless of whether the SAE/SARs are considered related to the study intervention and/or the *in utero* drug exposure and subsequent NAS, they will be followed in a rigorous review process through the entire trial period. Clinical performance sites will be instructed to report all fatal events, unanticipated problems and other serious adverse events and suspected adverse reactions to the DSMB and IRB by secure email within 24 hours of first knowledge of the event. All SAES must be reported to NIDA within 72 hours. Additionally, all current study data for that particular subject will be entered to allow for timely review by the External Medical Safety Monitor (EMSM).

The EMSM will closely monitor the incidence rates of all adverse events reported, whether serious or not, throughout the study, and will alert the DSMB if a trend is observed. A significant increase in the rate of adverse events in the SVS treatment group would be cause for concern for the safety of participants in the study. Information on adverse events will be presented in several ways: (1) Listings of serious adverse events with accompanying narrative summary by the Safety Officer with input from the Study PI; (2) Summaries of adverse events by body system and type of event. This information will be presented by blinded treatment group (i.e., SVS and SCC) to the DSMB for each group. In addition, the Safety Officer will be given treatment information in a blinded fashion, although he/she can request to be unblinded in cases where that knowledge could be critical.

Serious adverse events should not be reported for hospitalization or prolonged hospitalization in the following scenarios: for a diagnostic or elective surgical procedure related to a preexisting condition; to allow for an efficacy measure for the study; or, for a planned surgical procedure that was not the result of a condition worsening due to participation in the study.

A summary of all AEs and SAEs, a summary of all reports, and a coded list of all subjects who were terminated from the study due to study-related adverse events, will be included in reports submitted by the DSMB to the IRBs. An annual report will be submitted to the IRBs at all participating sites. NIH NIDA will also receive all reports.

6.1.1. Definitions.

http://www.accessdata.fda.gov/scripts/cdrh/cfdocs/cfcfr/CFRSearch.cfm?fr=56.102 The clinical site investigator, on the basis of his or her clinical judgment and the following definitions, determines the relationship of the adverse event to the protocol intervention as one of the following:

- Definitely: Any adverse reaction and those adverse events that cannot be reasonably explained by an alternative explanation, e.g., concomitant drug(s), concomitant disease(s). The relationship in time is very suggestive, e.g., improvement coinciding with discontinuation and recurrence on reinstitution.
- Probably: An AE that might be due to the use of the study intervention. The relationship in time is suggestive, e.g., improvement coinciding with discontinuation. An alternative explanation is less likely, e.g., concomitant drug(s), concomitant disease(s); and, other causes have been eliminated or are unlikely.
- Possibly: An AE that might be due to the use of the study intervention. An alternative explanation, e.g., concomitant drug(s), concomitant disease(s) is inconclusive. The relationship in time is reasonable; therefore, the causal relationship cannot be excluded and while other potential causes may or may not exist, a causal relationship to the study drug does not appear probable.

6.1.2. Adverse Event Follow-Up. Subjects with adverse events (both serious and non-serious) will be followed as clinically indicated and no less often than specified by this protocol for standard follow-up of subjects enrolled in the study. At those visits, updated information on the adverse event will be collected and entered into the REDCap data capture system until the adverse event is completely resolved.

6.2 Reporting of IRB Actions to NIDA

All actions of the UMMS or U Pitt IRBs related to the conduct of this study will be reported to the NIDA Project Officer immediately. Any additional follow-up will be discussed at that time.

6.3 Reporting of Changes or Amendments to the Protocol

This study will be conducted in compliance with the protocol approved by the Institutional Review Board and according to Good Clinical Practice standards. No deviation from the protocol will be implemented without the prior review and approval of the IRB except where it may be necessary to eliminate an immediate hazard to a research subject. In such case, the deviation will be reported to the IRB as soon as possible. Any change or amendment to the protocol must have prior approval from NIDA PO.

6.4 Trial Stopping Rules

There will be no formal statistical stopping boundaries proposed for this study, although the DSMB can request such boundaries be determined at any time during the study for both safety and efficacy (including futility). However, an apparent, consistent and persistent evidence of net harm that tends to overwhelm any benefit may allow for premature termination of the study. Continuing enrollment into each cohort will be determined in an ongoing basis and at periodic intervals. The DSMB will receive a report on all reported AEs and SAEs as well as the proportion of subjects with any specific event of interest. The finding of any unexpected serious adverse event considered to be related to study intervention in 2 of 6 patients will lead to review and suspension of recruitment and review of the complete data by the External Medical Safety Monitor (EMSM).

Following the EMSM's review, the safety report (and any comments from the EMSM) will be sent to the DSMB. The DSMB will make the final recommendation for early termination versus continuation of the study after reviewing the available data. The decision will be guided by safety. In addition to the planned evaluations, the EMSM and DSMB will receive quarterly safety summary reports of enrollment, baseline demographics, withdrawals from treatment and all AEs and SAEs with information on relation to study treatment.

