1.1 Trial Objectives

This study investigates Stochastic Vibrotactile Stimulation (SVS) complementary to standard of care for treating NAS. Using a specially-constructed crib mattress we will determine if SVS reduces symptoms and duration of NAS and improves long term outcomes in intrauterine opioid-exposed newborns. Findings from this study will elucidate whether SVS has potential as a therapeutic treatment for drug-exposed newborns to reduce symptomatology, facilitate weaning and minimize hospitalization, with implications for better regulation of systems and improved developmental outcomes.

1.1.1. Specific Aims. The three areas to be investigated in this project are:

Specific Aim 1. Determine the efficacy of SVS as a non-pharmacological therapy complementary to standard clinical care (SCC) for reducing severity and duration of opioid withdrawal in newborns compared to SCC alone. Quantify clinical variables: NAS severity/administration of treatment, treatment days, days in hospital, velocity of weight gain, cumulative morphine dose, and longitudinal assessment of movement activity.

Specific Aim 2. Examine physiological responses to SVS compared to SCC at two stages of withdrawal severity. Measure cardio-respiratory stability, temperature regulation, and movement activity.

Specific Aim 3. Compare neurobehavioral outcomes in fetal drug-exposed infants between infants who received SVS and those who received SCC. Examine longitudinal outcomes assessments at 1 month, 6-months and 1 year to test whether early intervention with SVS compared to SCC improves physical, social, emotional and cognitive development.

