4.3.2 Specific Aim 1: We will use mixed effects models as described above to examine whether infants treated with SVS compared to SCC have: 1) Lower daily average and maximum NAS scores; 2) Less morphine requirement (primary pharmacological treatment for managing NAS at both sites; cumulative dose normalized for body weight); 3) Enhanced velocity of weight gain throughout hospitalization; and 4) Shorter hospitalization length of stay. A model will be fit for each outcome using Nagelkerke's R² to determine the model with the best fit using the ratio of the -2 log likelihoods for the model with covariates compared to the intercept-only model. Factors of interest will be included in the model as appropriate and interactions with treatment group will be tested as well. The interactions will indicate whether the treatment effect is the same across subgroups. Additional analyses to identify groups of infants who do particularly well (or poorly) with SVS will be conducted using latent class techniques, such as cluster analysis (for continuous variables) or latent class analysis (for discrete variables). The factors of interest will include: drug exposure (e.g., prescribed maintenance therapy, prescription drugs and illicit substance; with or without poly-drug use), demographic data (gender, race, gestational age, birth weight, birth head circumference, delivery mode, anesthesia at delivery), and feed type (formula or breast milk).

Movement: Actigraphy (movement activity frequency) will be compared across days and between Groups using similar mixed effects models as above. The outcomes of interest are actigraphy throughout hospitalization to determine if SVS reduces movement and increases quiescence episodes over time (12 and 24 hour assessments) compared to SCC.

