7.2 Collection and Reporting of AEs and SAEs

Adverse events, as defined in the protocol, will be collected from the date and time of randomization to the date and time of hospital discharge as discussed above in

Section 6.1. All adverse events will be coded using MedDRA and will be reported to the DSMB in tabular form organized by patient, showing the adverse event with the preferred term grouped within system organ class as well as relatedness to the treatment. Tables will show the treatment-emergent adverse events, i.e., adverse events that occurred after randomization or worsened after randomization. These tables will be reviewed at every DSMB meeting (and more frequently if requested).

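### Adverse-event counts and proportions are not adjusted for time at risk, so they could understate SVS risk if SVS shortens hospital stay

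*Combined protocol and SAP*

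**What the plan says.** **Collection window.** Section 7.2 states that adverse events "will be collected from the date and time of randomization to the date and time of hospital discharge". No fixed number of days is set.

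**What the safety reviewers receive.** Under 6.4 the DSMB gets a report on all AEs and SAEs "as well as the proportion of subjects with any specific event of interest", and the External Medical Safety Monitor (EMSM) and DSMB also get quarterly safety summaries. Section 6.1 has the EMSM "closely monitor the incidence rates of all adverse events reported" and alert the DSMB to a trend, without defining the denominator. On presentation by arm, 6.1 says: "This information will be presented by blinded treatment group (i.e., SVS and SCC) to the DSMB for each group".

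**The comparison that matters.** Section 6.1 says: "A significant increase in the rate of adverse events in the SVS treatment group would be cause for concern". It names no test, denominator or exposure adjustment. Section 6.4 sets no formal boundaries and leaves early termination to a judgment of harm against benefit.

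**Expected effect on stay.** Section 1.1 hopes that SVS will "facilitate weaning and minimize hospitalization". Section 4.3.2 tests for "Shorter hospitalization length of stay", and Table 1 lists hospital duration among the Aim 1 primary clinical outcomes.

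**A second statement on the period.** Of SAEs and suspected adverse reactions, 6.1 says "they will be followed in a rigorous review process through the entire trial period". Section 7.2, which refers back to 6.1, ends collection at discharge.

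**The concern.** The window closes at discharge, a post-randomization event that the treatment is meant to move. If the trial's own hypothesis on length of stay is right, SVS infants are observed for fewer days than SCC infants. A proportion of infants with an event, or a raw count, then mixes the daily risk with the number of days watched. An equal daily risk can look lower under SVS, and a higher one can look equal. If SVS lengthened stay, the distortion would run the other way and suggest harm.

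The point concerns in-hospital events and does not depend on what happens after discharge. It matters because, without formal boundaries, the DSMB judges patterns between the arms, and no planned summary separates risk from time at risk.

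**Working it through.** **Inputs from the documents.** 1:1 allocation (2.1.2); 115 infants per group (2.4.1); AE window from randomization to discharge (7.2); shorter stay hypothesised (1.1, 4.3.2). The documents give no length of stay, AE rate or safety power, so those below are assumptions.

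**The plan's own figure.** The only relevant one is the group size. The difference detectable with 90% power at SD 2.5 is 2.5 × (1.960 + 1.282) × √(2/115) = 1.07, which rounds to the stated 1.1; power at 1.1 is 0.916. The figure reproduces, so 115 per arm is used as the safety denominator.

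**Equal constant daily hazard in both arms.** Let p be the SCC proportion with an event and r the SVS/SCC ratio of stay. The SVS proportion is 1 − (1 − p)^r. With p = 20%:

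| r | SVS proportion | Apparent risk ratio | Infants of 115 (SCC vs SVS) | Chance that p < 0.05 |
|---|---|---|---|---|
| 0.9 | 18.2% | 0.91 | 23 vs 21 | 5% |
| 0.8 | 16.4% | 0.82 | 23 vs 19 | 11% |
| 0.7 | 14.5% | 0.72 | 23 vs 17 | 20% |

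For p from 5% to 50% at r = 0.8, the ratio runs from 0.80 to 0.85.

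**The same in days.** Proportion = 1 − exp(−h × L). With h = 2% per day, 20 days gives 1 − exp(−0.40) = 33.0% and 16 days gives 1 − exp(−0.32) = 27.4%, a ratio of 0.83. With h = 0.5% per day the figures are 9.5% and 7.7%. Over stays of 10 to 30 days, reductions of 10 to 30% and h of 0.5 or 2%, the ratio is 0.71 to 0.92.

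**Masked harm.** A true hazard ratio of 1/r leaves the proportions equal: 1.11, 1.25 and 1.43 for r = 0.9, 0.8 and 0.7. With p = 20% and r = 0.8, a true hazard ratio of 1.25 shows as 20.0% vs 20.0%. Over the full SCC window it would show as 1 − 0.8^1.25 = 24.3%.

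**Sensitivity.** Gamma-distributed stays (coefficient of variation 0.5 to 0.8) give 16.4 to 16.6% at r = 0.8, so variation in stay hardly matters. Timing of events does. Put 80% of the hazard in the first 5 days of a 20-day stay, with stay cut to 16 days. The SVS arm then accrues 0.8 + 0.2 × 11/15 = 0.947 of the SCC cumulative hazard, giving 19.0% vs 20.0%, a ratio of 0.95. If all events fall while both arms are in hospital, or if r = 1, there is no bias.

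**Checking possible remedies.**
- *One overall rate per infant-day.* This is exact under constant hazard. In the front-loaded case it overcorrects: 0.947/0.8 = 1.18 against SVS with no true difference.
- *Rates within day-of-life bands.* Suppose half the infants are mild (0.5% per day) and half severe (2% per day), with no SVS effect on risk, and SVS discharges mild infants after day 10 while all others stay past day 14. For days 8 to 14 the SCC rate is (0.5 + 2)/2 = 1.25% per day. The SVS rate is (3 × 0.5 + 7 × 2)/10 = 1.55%, a false ratio of 1.24.
- *A common early window.* While nearly all infants in both arms remain in hospital, time at risk is nearly equal and selection by discharge is negligible. It cannot show late harm.

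No single column is enough; they need to be read together.

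**The case against.** A reader might infer that SVS would look safer simply because infants leave sooner, or that the DSMB sees only a proportion. The documents support neither. The bias needs SVS to shorten stay and events to persist late into the stay, and neither is established. The DSMB also receives all AEs and SAEs, tables organized by patient with relatedness, and SAE listings with narratives. The EMSM watches incidence rates, which could in principle be per infant-day.

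Other points on that side are fair. SVS exposure also ends at discharge, so the in-hospital proportion validly describes in-hospital risk, and fewer in-hospital events after earlier discharge may be a real consequence of treatment. For SAEs the discharge cut-off is unsettled, because 6.1 can be read as covering the whole trial. The trigger of 2 in 6 patients in 6.4 is not a between-arm comparison, so this bias does not act on it in the same way. The DSMB may request boundaries at any time. Section 7.1.1 reports no known mattress risks.

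These points limit the size and certainty of the problem but do not remove it. Raw counts carry the same bias as proportions, an undefined rate guarantees no adjustment, and narratives do not supply a denominator.

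**Conclusion.** The point holds in conditional form. Non-serious adverse events are collected only to discharge, discharge is expected to depend on treatment, and no written summary accounts for time at risk. If SVS shortens stay and events continue through it, counts and proportions could understate SVS risk.

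The size cannot be derived from the documents. For an assumed 20% shorter stay it ranges from an apparent risk ratio of about 0.82 to 0.83 under constant hazard, enough to hide a true hazard ratio of 1.25, to about 0.95 when events cluster early. With unchanged stay it is nil. At 115 per arm the artefact would seldom reach significance on its own (5 to 20% for p = 20%), so the main risk is a muted harm signal rather than a false claim of safety.

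**What to change.** In 6.1, 6.4 and 7.2:

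1. Keep the proportion of infants with an event. Beside it, by arm, report events per infant-day with the infant-days and numbers at risk, and state that this is the denominator meant by incidence rates in 6.1.
2. Add the proportion with an event over a common early window in which nearly all infants in both arms are still in hospital. Choose its length from pooled length-of-stay data, without reference to arm.
3. Day-of-life bands may be shown, but label the later ones descriptive. They hold only infants not yet discharged, are open to post-randomization selection, and will have sparse cells.
4. Reconcile the SAE and suspected-adverse-reaction period in 6.1 with the discharge cut-off in 7.2. Say whether the post-discharge calls in 4.1.3, which run to 14 months, collect adverse events.

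Items 1 to 3 change table shells and definitions only, with no added infants, visits or procedures. Day of life at discharge is an outcome in Table 1. The treatment-emergent tables in 7.2 already imply event timing relative to randomization, but no AE onset-date field is listed, so its capture should be confirmed. Item 4 costs more only if it extends collection beyond discharge. Protocol changes need IRB and NIDA approval under 6.3.

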6.5 Disclosure of any conflict of interest (COI) in the DSMP

Conflict of Interest. The PI ([name]) is a co-inventor on a patent for use of the uniquely constructed mattress that delivers the SVS. There is an approved mitigation plan in place at UMass due to a potential financial conflict of interest: 1) [name] will not be involved in enrolling or consenting clinical study participants; 2) The consent will convey potential financial interest in the clinical study; 3) Data analysis will be subject to a biannual Quality Assurance review by a suitable member of the UMMS human research protection program not otherwise associated with the Clinical Study. We will obtain required approvals for [name] to conduct studies at UPitt as per the Conflict of Interest Committee requirements at UPitt.

